Study Protocol

Official Title: Effects of Amygdala Neurofeedback on Depressive Symptoms and Processing Biases

ClinicalTrials.gov ID (NCT number): NCT02709161

Protocol Date: 10/05/2021

Scientific Background

Real-time functional magnetic resonance imaging (rtfMRI), in which blood oxygen-level dependent (BOLD) fMRI data processing and display are performed concomitant with image acquisition (Cox et al., 1995) has enabled rtfMRI neurofeedback (rtfMRI-nf), allowing a person to see and regulate the fMRI signal from their own brain (deCharms, 2008). rtfMRI-nf has the advantage over other biofeedback methods (such as EEG) of precisely localizing neurophysiological activation, and allowing focal investigation of relationships between cognitive-behavioral functions and neuroplasticity changes in deep brain structures (deCharms et al., 2004; Weiskopf et al., 2007). Recent studies provide evidence of the utility of rtfMRI-nf in psychiatric populations (Ruiz et al., 2011; Linden et al., 2012; Young et al., 2014). Our proposal focuses on attenuated positive emotional processing in major depressive disorder (MDD). Cognitive theories of MDD are predicated on the idea that perception and cognition are biased by negative emotions (Roiser et al., 2012), and abundant evidence suggests left amygdala hemodynamic responses are exaggerated to negative stimuli in MDD (Sheline et al., 2001; Drevets et al., 2002; Siegle et al., 2002; Fu et al., 2004). However, extant evidence further suggests MDD-associated abnormalities are “doubly dissociated” from healthy individuals by virtue of their greater amygdala response to negative stimuli and attenuated amygdala response to positive stimuli (Victor et al., 2010), including positive autobiographical memories (Young et al., 2016). [name] previous work has shown that it is possible to restore the normative positive processing bias evinced in healthy individuals to MDD patients via the use of rtfMRI-nf (Young et al., 2014). This research suggests that low amygdala automatic reactivity to positive stimuli is associated with reduced recruitment of attentional resources that cause emotional stimuli to be rendered salient and something worth expending effort recalling, suggesting neurocognitive techniques increasing positive processing conceivably hold therapeutic potential in the clinical management of MDD.

Neurofeedback combines biological and cognitive treatment principles in a way that differentiates it from both traditional biofeedback and cognitive therapy. It provides the additional benefit of enhancing the patient's perception of self-efficacy, which is considered an important principle in cognitive restructuring (Bandura, 1997). A fundamental component of cognitive-behavioral treatment of MDD involves the restructuring of thought and emotional processing towards affectively positive and away from affectively negative thoughts, feelings, and memories (Beck, 1993). Newer cognitive therapies specifically target positive affect and increasing patients' ability to sustain positive affect over time (McMakin et al., 2011). The continued focus on improving positive affect as a component of cognitive therapy provides a clear rationale to train MDD patients to more effectively access positive autobiographical memories in the generation of positive mood. The rtfMRI-nf procedure for MDD may provide clinicians with a tool to optimize cognitive therapy. It is a well-established finding in the literature that CBT is associated with better outcome when patients experience ‘sudden gains’ during the first third of treatment. A sudden gain is defined as a change in Beck Depression Inventory (BDI) score in one between session interval that is at least 7 points and at least 25% of the previous score (Tang & DeRubies, 1999; Kelly et al., 2005). While the neurophysiological mechanism underlying this phenomenon has not to our knowledge been investigated it has been established that these gains can occur in the absence of overt cognitive changes (Kelly et al., 2005). Patients who experience a sudden gain during the first third of treatment are more likely to be classified as treatment responders (Kelly et al., 2005), and experience better outcomes, with

patients experiencing sudden gains remaining less depressed than other patients after the end of treatment (Tang & DeRubeis, 1999; Tang et al., 2002; Tang et al., 2007). Therefore, increasing the number of patients experience sudden gains during the first third of CBT has the potential to improve long-term outcomes of CBT and provides a strong rationale for augmenting CBT with early interventions that decrease depressive symptoms, such as our amygdala rtfMRI-nf protocol.

Study Objectives

The objective of the proposed research is to determine whether augmenting standard cognitive-behavioral therapy (CBT) with real-time fMRI neurofeedback aimed at increasing the amygdala's hemodynamic response to positive autobiographical memory recall will result in greater efficacy and a shorter time course to symptom improvement.

Specific Aim: In patients with major depressive disorder, determine whether the time course of symptom improvement and overall efficacy of cognitive-behavioral therapy (CBT) can be improved by augmenting it with real-time fMRI amygdala neurofeedback (rtfMRI-nf) regarding amygdala activity.

Hypothesis: Because our rtfMRI-nf procedure utilizes principles of CBT including restructuring emotional processing towards the positive, and because we have observed large changes in depression ratings over the course of 3 weeks in those receiving amygdala rtfMRI-nf, we hypothesize augmenting a course of CBT with two amygdala rtfMRI-nf sessions aimed at increasing the amygdala's response to positive autobiographical memories during the first month of therapy will result in a greater decrease in depressive symptoms (as measured by the primary outcome measure BDI-II and the secondary outcome measure PROMISE depression rating) compared to those who receive rtfMRI-nf from a parietal control region putatively not involved in emotional processing.

Study Design & Methods

We will assess the efficacy of augmenting cognitive behavioral therapy with real-time fMRI neurofeedback in depressed adults. This is an experimental longitudinal design where participants will be followed weekly for 10 weeks after being randomized under double-blind conditions to receive 2 sessions of neurofeedback from the amygdala (experimental group) or a parietal region serving as an active control. Procedures involve a battery of self-report measures, fMRI and psychophysiological indices (eye tracking, heart rate, respiration, electroencephalography). Following the neurofeedback procedure, participants will receive 10 weeks of CBT at no cost to them. Two hundred and forty participants will be screened, and 60 will complete the research activities.

Eligibility Criteria

- i) right-handed adults (ages 18 – 55) with a primary diagnosis of MDD according to diagnostic criteria DSM-IV-TR for recurrent MDD who are currently depressed will be recruited to participate
- ii) must be able to give written informed consent prior to participation
- iii) Do not have a clinically significant or unstable cardiovascular, pulmonary, endocrine, neurological, gastrointestinal illness or unstable medical disorder
- iv) Do not meet DSM-IV criteria for alcohol and/or substance dependence (other than nicotine) within 12 months prior to screening
- v) Do not have a history of traumatic brain injury
- vi) Are able to complete MRI scan; do not have claustrophobia or general MRI exclusions (e.g., shrapnel inside body)
- vii) are not currently pregnant or breast feeding
- viii) are able to complete questionnaires written in English
- ix) Are not currently (within 3 weeks of testing) using any anticonvulsants, stimulants, benzodiazepines, beta-blockers, or other medications (except antidepressants and antipsychotics) likely to influence cerebral blood flow. Effective medications will not be discontinued for the purposes of the study.
- x) Do not have a DSM-IV-TR diagnosis of psychotic or organic mental disorder, bipolar I or II disorder. We will record the presence of co-morbid anxiety disorders, but will not exclude MDD participants with such disorders so long as the anxiety disorder is not the primary/dominant diagnosis
- xi) Do not have any eye problems or difficulties in corrected vision.
- xii) are willing to temporarily discontinue therapy to participate in the study

Statistical Considerations

To examine change in BDI score (primary outcome) and PROMIS (secondary outcome), a linear mixed effects model with the fixed factors of Visit(1, 2, 3, 4) and Group(Experimental, Control) was used. The neurofeedback training effect was evaluated via linear mixed effects model with the fixed factors of Run(Baseline, Practice, Run1, Run2, Run3, Transfer), Visit(2, 3), region-of-interest(Amygdala, Intraparietal), and Group(Experimental, Control) for regional percent signal change.

Power analysis used in estimating sample size in fMRI studies suggests for a liberal threshold of $p < 0.05$, 16 participants are required to achieve 80% power at the single voxel level for typical activations between groups (Desmond et al., 2002) Mumford & Nichols, 2008). Proof-of-concept studies comparing CBT for MDD augmented with antidepressant medication have found statistical differences on clinical measures (including HDRS and BDI) with 20 participants per group (Rush et al., 1977; Blackburn et al., 1981; Lynch et al., 2003; Huijbers et al., 2012). Therefore, during the R00 phase, we plan to include 30 participants per group to allow for larger drop out rates (at least 33%) due to the increased number of study visits required for the CBT component.

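### Primary BDI-II model: state the Visit-by-Group term, adjust it for Visit 1 BDI, and name one deciding test

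*Combined protocol and SAP*

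**What the plan says.** Under Study Objectives, the hypothesis is that amygdala neurofeedback "will result in a greater decrease in depressive symptoms (as measured by the primary outcome measure BDI-II", with PROMIS depression as secondary. The objective looks for "greater efficacy and a shorter time course to symptom improvement", and the Specific Aim is to "determine whether the time course of symptom improvement and overall efficacy of cognitive-behavioral therapy (CBT) can be improved". The target is therefore a between-group difference in change, and speed of improvement is part of it.

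Statistical Considerations holds the only analysis text. Its purpose clause reads "To examine change in BDI score (primary outcome) and PROMIS (secondary outcome", followed by a linear mixed effects model "with the fixed factors of Visit(1, 2, 3, 4) and Group(Experimental, Control) was used". The neurofeedback training model is described in the same factor-list style, with "Run(Baseline, Practice, Run1, Run2, Run3, Transfer), Visit(2, 3" among its factors.

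For BDI, the documents name no Visit-by-Group term, deciding visit or contrast, test level, covariance structure, or use of the Visit 1 score as a covariate or constraint. Visit 1 appears only as one of the four levels of Visit. Visits 1 to 4 are not mapped to the weekly follow-up in Study Design & Methods.

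**The concern.** A difference in change between arms is carried by the Visit-by-Group interaction, or by a contrast built from it. The text names neither, so a reader cannot tell which number decides the trial. Two readings fit the text:

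- **Full factorial.** The interaction answers the right question. However, each contrast of change from Visit 1 carries the full sampling error of the Visit 1 difference between arms. Randomisation makes that difference zero in expectation, so leaving it free costs precision.
- **Literally additive.** There is no parameter for a difference in change. The Group coefficient is the mean arm difference over all four visits, including one that appears to precede neurofeedback, so an effect that begins later is diluted.

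The trial is small, and no BDI power calculation shows any margin to spare. Precision lost through the choice of model is worth recovering.

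**Working it through.** **The plan's own figure.** The sample size paragraph takes 20 per group from earlier studies and allows for dropout: "we plan to include 30 participants per group to allow for larger drop out rates (at least 33"%). 20/(1 − 0.33) = 29.85, which rounds up to 30, so the figure reproduces. In reverse, 30 × 0.67 = 20.1, so I use 20 completers per arm. This concern does not affect the figure.

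**Assumed inputs (none given for BDI).** Four visits; compound symmetry with correlation ρ = 0.3, 0.5 or 0.7; SD 1 at each visit; no arm difference at Visit 1; two-sided 5%. For power only, the largest arm difference is d = 0.8 SD.

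**Step 1: precision, with no effect size needed.**
- One visit: the per-arm variance is 2(1 − ρ) for unadjusted change and 1 − ρ² after baseline adjustment. The ratio is 2/(1 + ρ) = 1.54, 1.33, 1.18.
- Mean of Visits 2–4: 4(1 − ρ)/3 against (1 + 2ρ)/3 − ρ². The ratio is 4/(1 + 3ρ) = 2.11, 1.60, 1.29.

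**Step 2: sensitivity to equal SDs.** Entry requires current depression, which may narrow the Visit 1 spread. With k = Visit 1 SD over later SD, the one-visit ratio is (1 + k² − 2ρk)/(1 − ρ²).
- k = 0.8: 1.28, 1.12, 1.02.
- k = 0.7: 1.07/0.91 = 1.18, 0.79/0.75 = 1.05, 0.51/0.51 = 1.00.

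**Step 3: the same 3-df test with and without adjustment.** Let δ be the vector of arm differences and n = 20 per arm.
- Unadjusted: λ = (n/2) Σ(δj − mean δ)²/(1 − ρ), over Visits 1–4, with 38 × 3 = 114 error df.
- Adjusted: λ = (n/2)[Σδj² − ρ/(1 + 3ρ) × (Σδj)²]/(1 − ρ), over Visits 2–4, with 37 × 3 = 111 error df.

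Example: linear growth (0, 1/3, 2/3, 1) × 0.8 and ρ = 0.5. Unadjusted λ = 10 × 0.3556/0.5 = 7.11, power 58%. Adjusted λ = 10 × (0.9956 − 0.2 × 2.56)/0.5 = 9.67, power 73%.

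Power in percent; each range runs from ρ = 0.3 to ρ = 0.7:

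| Effect pattern | Unadjusted 3-df | Adjusted 3-df | Adjusted mean, Visits 2–4 | Adjusted Visit 4 |
|---|---|---|---|---|
| Linear growth | 43–82 | 66–88 | 69–84 | 73–93 |
| Visit 4 only | 56–93 | 62–93 | 23–31 | 73–93 |
| Full from Visit 3 | 70–98 | 84–99 | 69–84 | 73–93 |
| Visits 2–3 only (faster, same end) | 70–98 | 84–99 | 69–84 | 5 |
| Full from Visit 2 | 56–93 | 90–98 | 96–99 | 73–93 |

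The adjusted 3-df test beats its unadjusted counterpart in every row. The gain is smallest for an effect at Visit 4 only with ρ = 0.7 (92.5% to 93.3%). The last two columns show that no single adjusted contrast is best for every pattern.

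**Step 4: the additive reading, if it applied.** The Group coefficient recovers the average of the pattern: (0 + 1/3 + 2/3 + 1)/4 = 50% of the final effect under linear growth, 25% if the effect is at Visit 4 only, 50% if full from Visit 3, and 75% if full from Visit 2. Under linear growth its power is 29–43%.

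**The case against.** The strongest reply is that the text is shorthand. The stated purpose is to examine change, and an additive version of the training model could not test region-specific training by arm, so both factor lists are most naturally full factorials. That stands, and it limits the point in several ways.

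- A reader might infer that the interaction was omitted and that the primary model cannot test the hypothesis. The documents do not establish this. The dilution in Step 4 depends on the less plausible reading, and even there the Group test remains a valid test of no effect.
- A reader might infer a change-score analysis. That does not fit, because change from Visit 1 would be zero for everyone at a listed level of Visit.
- A reader might infer a false-positive rate near 10% (1 − 0.95² = 9.75%). That needs either the Group term or the interaction to count as success. No passage says so, and the hypothesis points to change.
- A reader might turn the ratios into a shortfall of 18–54% in participants. That holds only with equal SDs and only if an unadjusted change contrast decides. Neither is stated.

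It is also fair to say that replacing the 3-df interaction with an average over visits is not a uniform gain. The average falls to 23–31% power for an effect at Visit 4 only, where the unadjusted interaction has 56–93%. This is why the like-for-like comparison is the adjusted and unadjusted versions of the same test.

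What remains is that the deciding test is unnamed and that the Visit 1 score is not used to sharpen it.

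**Conclusion.** The point holds as an under-specified primary analysis with an available gain in precision. It does not show an invalid test. On the likelier factorial reading, adjusting for Visit 1 BDI reduces variance at no cost in data: the unadjusted one-visit variance is 1.18 to 1.54 times the adjusted one with equal SDs, and 1.00 to 1.18 times with a Visit 1 SD ratio of 0.7. The adjusted 3-df test was at least as powerful in all five patterns examined, with gains from under 1 percentage point to about 33 (56% to 90%, full from Visit 2, ρ = 0.3).

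This rests on compound symmetry, the assumed ρ, and Visit 1 preceding neurofeedback. The last is inferred from the training model using Visits 2 and 3. All power figures also assume d = 0.8 and 20 completers per arm, so they illustrate relative performance and do not estimate this trial's power.

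**What to change.** 1. State that Visit, Group and Visit-by-Group are fitted for BDI-II and PROMIS, with the Visit 1 score either as a covariate or kept as a response with the arms constrained equal at Visit 1. With the covariate form, the responses are Visits 2–4, and the joint test must take Group and Visit-by-Group together. The interaction alone would miss a constant effect.
2. Confirm that Visit 1 BDI precedes neurofeedback, say whether Visit 2 BDI is taken before or after scanning, and map Visits 1–4 to study weeks. The adjustment depends on the first of these.
3. Name one baseline-adjusted BDI-II test, with its level, as primary. A joint test over post-neurofeedback visits, their average, or one visit are all defensible, and the choice is the sponsor's. The average is weak if the effect appears only at Visit 4. A single late visit misses an effect that is only faster, which matters because time course is in the aim.
4. Label the all-visit Group term, the remaining contrasts and PROMIS as secondary.

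The data and software stay the same. Before analysis, only the wording and model code change. The past tense in Statistical Considerations suggests that the analysis may already be done. If so, report the baseline-adjusted test and say when the primary term was fixed. Such a re-analysis could not be called prespecified.
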